**11.6 \* Secondary Outcome(s)**

Indicate which *additional variable(s)* will be assessed to judge the secondary outcome(s). Give measurement units, if applicable.

Gene expression profile  
Cytokines  
Chemokines

**11.7 \* Methods and Procedures**

Please provide a description of the laboratory and clinical analyses and procedures that will be performed. Include the role of external collaborators and consultants when appropriate.

Participants will be seen at Rockefeller University as outpatients. There will be two (2) cohorts, namely those with the metabolic Syndrome who have not been treated and healthy volunteers.

The Metabolic Syndrome will be determined according to the NHLBI Guidelines.

**SCREENING VISIT #1**

Consent

Medical history

Physical examination including height and weight to determine BMI, and waist circumference

Vital Signs - If the initial blood pressure is above 150/90 mmHg upon arrival to the OPRC, a second B/P will be taken by the LIP during the screening process. The average of the two readings will be the enrollment criterion.

POCT - HIV

POCT - urine pregnancy test

Labs: HbA1c - (1) 3.0 ml lavender tube

Hepatitis Panel - (1) 8.5ml SST marble top tube

Comprehensive metabolic & CRP - (1) 8.5 ml SST marble top tube

CBC - 3 ml lavender top tube

Gene expression - (3) 2.5ml Pax RNA tube (total 7.5ml).

Influenza A & B antibodies - (1) 10ml red top tube

Total blood volume to be drawn for screening visit 1 = 40.5ml .

Instructions to return fasting for 8 hours prior to the next visit.

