**SCREENING VISIT #2 (within 2 weeks of screening visit #1)**

Adverse event assessment

Fasting Labs: Glucose, lipids and triglycerides) - (1) 3.5ml gold top tube

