**Order Number    Criteria**

**METABOLIC SYNDROME COHORT**

Any evidence of NHLBI Guidelines for Clinical Identification of the Metabolic Syndrome: (must have 3 or more of the following risk factors):

Abdominal Obesity, given as a waist circumference:

- Men >102 cm (>40 in)
- Women > 88 cm (>35 in)

Triglycerides  $\geq 150$  mg/dl

HDL Cholesterol:

- Men < 40 mg/dl
- Women <50 mg/dl

Blood Pressure  $\geq 130/ \geq 85$  mm Hg or on antihypertensive medication

Fasting Glucose  $\geq 100$  mg/dl

1

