**Order Number    Criteria**

1                      Currently undergoing treatment for the metabolic syndrome

2                      Blood Pressure > 150/90

- 3 NSAIDs and/or Aspirin ingestion within the last 14 days
- 4 Hepatitis A, B and C
- 4 Self-reported history of any active autoimmune diseases
- 5 Self-reported ingestion of statins within the last 3 months
- 6 Self-reported antibiotic use within the last 3 months
- 7 Anti-inflammatories including biologics and corticosteroids within last 3 months( nasal spray and topical applications are OK)or Omega 3 Fatty Acids.
- 8 Self-reported hx of cancer treatment within the last year
- 9 Allergy to eggs
- 10 History of Guillain-Barre syndrome
- 11 Pregnant ( determined by POCT at Screening visit #1 and Study visit #1).
- 12 HIV positive
- 13 Self-reported history of receiving the flu vaccination after June 1, 2016.
- 14 Any self-reported infection in the week of the visit except the first two visits (Screening visit 1 and Screening visit 2) and the last visit (Study visit #5) that could be rescheduled.
- 15 Any medical, psychological or social condition that, in the opinion of the Investigator, would jeopardize the health or well-being of the participant during any study procedures or the integrity of the data.

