### 13.0 Study Plan

#### 13.1 \* Describe the study plan:

Select a template:  Select an arm:

Procedure/Task Name	CPT Code	Screening ...	Screening ...
Clinical Procedures			
Adverse Event Assessment			
Adverse Event /Serious Adverse Event Assessment			1
Assessments (Nursing)			
Assess for changes in general health status			1
Blood Pressure Seated		1	
Concomitant Medications			

\* What is the total number of outpatient visits for all subjects projected for the next year?

240

\* What is the average length of each outpatient visit (in hours)?

2

\* What is the total number of Day Patients visits for all subjects projected for the next year?

0

\* What is the average length of each Day Patient visit (in hours)?

0

\* What is the total number of inpatient days for all subjects projected for the next year?

0

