## 16.0 Recruitment and Advertising

**For assistance consult CRSO to create a robust Recruitment Plan see Help.**

### 16.1 \* What is the plan for recruitment?

**Overview:**

The CRROSS will prescreen up to 100 volunteers in order to enroll 20 with a metabolic syndrome and 20 healthy controls to achieve the goal of 40 evaluable participants at study completion. Healthy controls will be age matched (+/-5 years) and gender matched to the metabolic syndrome participants.

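### Below the 150/90 trigger, the 130/85 and 120/80 cohort limits are applied to a single arrival blood pressure; averaging two readings in every volunteer would cheaply reduce error at the edge of each cohort

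*Combined protocol and SAP*

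**What the plan says.** All references are to the combined protocol and SAP.

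- **Section 11.7, Screening Visit #1, Vital Signs.** The repeat is conditional: "If the initial blood pressure is above 150/90 mmHg upon arrival to the OPRC, a second B/P will be taken by the LIP". When it is taken, "The average of the two readings will be the enrollment criterion".
- **Section 12.12, exclusion 2.** The trigger is the same number as the exclusion limit: "Blood Pressure > 150/90".
- **Section 12.11, metabolic syndrome cohort.** A volunteer "must have 3 or more of the following risk factors". One of the five is blood pressure at or above 130/85, "or on antihypertensive medication".
- **Section 12.11, healthy controls.** Blood pressure must be at or below 120/80, together with limits on BMI, HDL, glucose, triglycerides and waist.
- **Section 11.7, Screening Visit #2.** It lists an adverse event assessment and "Fasting Labs: Glucose, lipids and triglycerides". No blood pressure is listed.
- **Section 13.1.** The visible part of the study plan has a row "Blood Pressure Seated" with one entry across the two screening columns. The grid is cut off in the text available.
- **Section 16.1.** The plan is to "prescreen up to 100 volunteers in order to enroll 20 with a metabolic syndrome and 20 healthy controls".

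**The concern.** The protocol accepts that one arrival reading is not good enough to exclude a volunteer at 150/90, and guards against it with a repeat and an average. It uses blood pressure at two other limits and calls for no repeat near either. Cohort is the exposure in every comparison, and there are 20 participants per group.

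Reading-to-reading noise acts in both directions at each limit. At 130/85, someone with exactly two other factors and no antihypertensive medication can be wrongly added to the metabolic syndrome cohort or wrongly left out. At 120/80, a true control can be rejected, or someone whose usual pressure is higher can be accepted. Wrong inclusions in either cohort tend to dilute the group difference.

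**Working it through.** The plan states no misclassification rate and no blood pressure SD, so there is no figure to reproduce. The distributions below are assumptions, shown as ranges.

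**1. Does the existing repeat help at the cohort limits?** Suppose the first systolic is just above 150. For the mean to reach 120, (150 + x)/2 ≤ 120 requires x below 90. For the mean to fall under 130, x must be below 110. For a first diastolic just above 90, the second must be below 70 for a mean of 80 or less, and below 80 for a mean under 85. The repeat therefore rarely decides a cohort limit.

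A paired systolic/diastolic simulation confirms this (400,000 draws per case; within-person SDs 5/4, 8/5 and 12/8 mmHg; correlation 0.5; repeat if either component exceeds its limit). For a volunteer whose usual pressure is 115/75, rejection as a control is:

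| SDs | Written rule | Single reading | Average of two for all |
|---|---|---|---|
| 5/4 | 21.9% | 21.9% | 10.3% |
| 8/5 | 33.6% | 33.6% | 22.6% |
| 12/8 | 44.4% | 44.7% | 36.0% |

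In the same model, and taking either component at its limit as enough, a person with usual pressure 125/80 is wrongly given the metabolic syndrome component in 22%, 33% and 42% of cases under the written rule. With averaging this becomes 10%, 23% and 36%.

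**2. Population-level error, systolic only.** Assume true systolic T ~ N(125, 14²) and one reading = T + N(0, s²), with s = 6 to 10 and no arrival effect. The average of two has error variance s²/2. Let v be the error variance, σ = √(196 + v) and ρ = 14/σ.

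- True controls rejected = 1 − Φ₂(−5/14, −5/σ; ρ)/Φ(−5/14).
- Share of those passing who are truly above 120 = 1 − Φ₂(−5/14, −5/σ; ρ)/Φ(−5/σ).
- Total passing = Φ(−5/σ).

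The few first readings above 150 are ignored in these three formulas. The false share at 130 comes from simulation with the written repeat rule applied.

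| Quantity | Written rule (s = 6 to 10) | Average of two |
|---|---|---|
| Counted ≥130 and not excluded, true value <130 | 20–31% | 15–24% |
| True controls (≤120) rejected | 15–23% | 11–18% |
| Passing ≤120, true value >120 | 18–28% | 13–21% |
| All volunteers passing ≤120 | 37.1–38.6% | 36.6–37.5% |

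The 15–24% uses the average at 150 as well. A rerun with the 150/90 exclusion kept as written gives 14–23%.

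**3. Number of controls passing.** With s = 6, the single reading has σ = √232 = 15.2 and Φ(−5/15.2) = 37.1%. The average has σ = √214 = 14.6 and Φ(−5/14.6) = 36.6%. Averaging rejects fewer true controls but stops slightly more false ones.

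If the first reading runs 5 mmHg high and the second does not, the means are 130 and 127.5. Passing then rises from Φ(−10/15.2) = 26% to Φ(−7.5/14.6) = 30%. For s = 10 it rises from 28% to 32%. Under that effect, false components at 130 fall from 35–42% to 24–32%, and true controls rejected fall from 34–37% to 21–26%.

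**4. Effect on the metabolic syndrome cohort.** Assume 20–40% of the 20 depend on this component.

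- Smallest gain: 20 × 0.20 × (0.20 − 0.15) = 0.2.
- Largest without an arrival effect: 20 × 0.40 × (0.31 − 0.24) = 0.6.
- Largest with one: 20 × 0.40 × (0.35 − 0.24) = 0.9.

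**The case against.** The case for leaving the rule alone has substance.

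- **Movement between cohorts.** A reader might infer that blood pressure error puts metabolic syndrome participants among the controls, or the reverse. It cannot. A control must be within every listed limit, and metabolic syndrome needs three abnormal factors. The error only admits or rejects at the edge of one cohort.
- **Recruitment.** A reader might infer that averaging eases the search for matched controls within a short season. Without an arrival effect the number passing is flat to slightly lower. It rises only if arrival readings run high, and nothing in the documents shows that they do.
- **Size.** Under one participant of 20 is small, and it rests on an assumed dependence on this component. Antihypertensive medication meets the component whatever the reading. With an assumed mean of 132, the no-arrival-effect false share under the written rule is 13–21% instead of 20–31%.
- **The study plan grid.** It is truncated and cannot show that no other reading is taken. Nothing in the text forbids one. What stands is that no section calls for one.
- **Side effects at 150/90.** Applying the average to everyone at the exclusion limit would change eligibility: 148 then 156 systolic passes now and would be excluded. About 0.5–1.3% of volunteers would be newly excluded. This is why the exclusion rule should stay as it is.
- **Systolic-only model.** The population percentages do not describe the paired limits exactly. The paired simulation points the same way for individual usual pressures.

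These points limit the size of the problem. They do not remove the mismatch between where the repeat applies and where cohort is decided.

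**Conclusion.** The point holds as a low-cost refinement and does not threaten the study's validity. For arrival readings at or below 150/90, the documents provide one reading to apply both cohort limits, and the existing repeat gives almost no protection there. In every scenario of the population model, averaging two readings lowered wrong inclusions at both limits and wrong rejections of controls. Under the assumed no-arrival-effect model, each error share falls by about 4 to 8 percentage points. The expected consequence is less than one of 20 metabolic syndrome participants, plus a more accurately selected control group that is not necessarily easier to fill. All of these sizes rest on assumed means and SDs. Only the rule and the limits come from the documents.

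**What to change.** In section 11.7, Screening Visit #1, replace the conditional wording with text to this effect: take two seated blood pressure readings in every volunteer; apply their average to the metabolic syndrome component and to the control limit in section 12.11; judge the 150/90 exclusion as now, on the first reading, or on the average when the first is above 150/90. Every numerical limit stays as written. The text should name the value used for each of the three limits, and say whether the licensed practitioner who now takes the repeat also takes the second reading in everyone.

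Cost: at an assumed 5 minutes per volunteer, 100 consents (section 12.8) × 5 minutes = 500 minutes, or about 8 hours of existing staff time. No visit or laboratory test is added. Volunteers already screened would have been classified on the conditional rule, so the record should show which rule applied to each participant.

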**STUDY VISIT #1 (Day 0) (within 1 month of screening visit #2)(+/- 1 week)**

Labs: venous blood sample for gene expression (3) 2.5ml Pax RNA tubes (total 7.5ml)

Cytokines (9ml for plasma (purple EDTA tube), 10 ml for serum (red top tube); **\*\*\*labs**

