**drawn prior to flu vaccine)**

POCT - urine pregnancy test

Adverse event assessment

Administration of the influenza vaccine intramuscularly (IM): Vaccination with quadrivalent 2016-2017 vaccine A/California/7/2009 (H1N1); A/Hong Kong/4801/2014 (H3N2); B/Brisbane/60/2008(B/Victoria lineage); B/Phuket/3073/2013 (B/Yamagata lineage). Participants of normal weight will be injected IM with a needle of 1 to 1.5 in length. Obese individuals (defined as BMI>25) generally will require the use of a 2 in length needle to assure that the injection reaches the muscle. The needle length used for injection will be documented in the medical record.

Total blood volume to be drawn for visit #1 = 26.5ml

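### The only pre-vaccination sample designated for influenza antibodies is taken at Screening Visit 1, up to 49 to 52 days before vaccination, and the plan does not say which visit supplies the baseline titer for seroconversion

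*Combined protocol and SAP*

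**What the plan says.** Section 11.7 gives the sampling schedule. At Screening Visit 1 it lists "Influenza A & B antibodies - (1) 10ml red top tube", and the visit total includes that tube: "Total blood volume to be drawn for screening visit 1 = 40.5ml". The same antibody line appears at Study Visit 4 (Day 28) and Study Visit 6 (Day 90).

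At Study Visit 1 (Day 0) there is no antibody line. The serum there belongs to another purpose: "Cytokines (9ml for plasma (purple EDTA tube), 10 ml for serum (red top tube". It is marked as "drawn prior to flu vaccine", and the visit closes with "Total blood volume to be drawn for visit #1 = 26.5ml".

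Two windows set the distance between the first antibody tube and the injection: "SCREENING VISIT #2 (within 2 weeks of screening visit #1" and "STUDY VISIT #1 (Day 0) (within 1 month of screening visit #2)(+/- 1 week".

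The Research Labs part of 11.7 calls for HI titers against each of the four vaccine strains and a neutralization assay, but ties neither to a visit or tube. Section 11.8 defines seroconversion by comparing a pre-vaccination with a post-vaccination HI titer, and likewise names no visit. Exclusion 14 in 12.12 covers "Any self-reported infection in the week of the visit except the first two visits (Screening visit 1 and Screening visit 2", and then adds the last visit and mentions rescheduling.

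**The concern.** Seroconversion is meant to capture the rise produced by the vaccine, so its starting value should describe the participant at vaccination. The one pre-vaccination sample that the schedule sets aside for antibodies can be weeks old by then, and the delay is free to vary from person to person. Section 16.1 ties recruitment to the influenza season, when titers can also move for reasons other than the study vaccine. The infection criterion gives limited protection: it rests on self-report and looks only at the week of a visit. An infection after Screening Visit 1 that is over more than a week before Day 0 falls outside it.

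What is at stake is whether individual participants are correctly classed as seroconverters, strain by strain, in a study with 20 per group. There is also a choice left open. Two sera could serve as baseline (three for someone who repeats screening under Visit 1-A), and nothing fixes in advance which one counts.

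**Working it through.** **Step 1. Reproduce the blood volumes, to see where an antibody tube is counted.** Inputs are the tube sizes in 11.7.

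| Visit | Tubes (ml) | Sum (ml) | Antibody tube listed |
|---|---|---|---|
| Screening 1 | 3 + 8.5 + 8.5 + 3 + 7.5 + 10 | 40.5 | yes |
| Screening 2 | 3.5 | 3.5 | no |
| Day 0 | 7.5 + 9 + 10 | 26.5 | no |
| Day 1 | 7.5 | 7.5 | no |
| Day 7 | 7.5 + 9 + 10 | 26.5 | no |
| Day 28 | 7.5 + 10 + 9 + 10 | 36.5 | yes |
| Day 90 | 7.5 + 10 + 9 + 10 | 36.5 | yes |

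Every visit total stated in the plan is matched. The sum is 40.5 + 3.5 + 26.5 + 7.5 + 26.5 + 36.5 + 36.5 = 177.5 ml, in line with the plan's figure of about 180 ml. Without the antibody tube Screening 1 would be 30.5 ml; with one, Day 0 would be 36.5 ml. So the tube is counted at Screening 1, and its absence at Day 0 shows in both the list and the total. At Day 28 and Day 90 the antibody tube comes in addition to the 10 ml cytokine serum, so on the plan's own pattern the Day 0 serum is not the antibody sample.

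**Step 2. Maximum gap from the Screening 1 tube to vaccination.** Gap = 14 days + one month + 7 days.

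- 28-day month: 14 + 28 + 7 = 49 days
- 30-day month: 14 + 30 + 7 = 51 days
- 31-day month: 14 + 31 + 7 = 52 days

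If the one-week allowance is not added, the range is 14 + 28 = 42 to 14 + 31 = 45 days. Adding the nominal 28 days after vaccination to the upper figures, the span from baseline to first post-vaccination titer can reach 49 + 28 = 77 to 52 + 28 = 80 days, instead of 28.

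**Step 3. Which endpoints use the baseline.**

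- Proportion with HI titer of at least 1:40 (11.8): no baseline term.
- Comparison of mean titers between groups (Statistical Analysis under 11.9): no change from baseline is mentioned.
- Seroconversion (11.8): uses the baseline twice, to choose the branch (below 1:10, or 1:10 and above) and as the denominator of the four-fold rise.

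**Step 4. How the choice of baseline can change a classification.** The titers here are hypothetical, chosen only to show the mechanism.

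- Screening 1:10, Day 0 1:40, Day 28 1:40. From screening the ratio is 40/10 = 4, a seroconverter. From Day 0 it is 40/40 = 1, not one.
- Screening 1:40, Day 0 1:10, Day 28 1:40. From screening the ratio is 40/40 = 1, not a seroconverter. From Day 0 it is 40/10 = 4, a seroconverter.

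A rise before Day 0 inflates the apparent response and a fall deflates it. The documents give no data on titer change over the gap, so neither the frequency nor the net direction can be computed.

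**The case against.** The strongest reply is that the plan never says seroconversion will be computed from the screening tube. The Research Labs text does not restrict the HI assay to one tube, and pre-vaccine serum exists on Day 0, so the laboratory could use it. A screening sample is also literally pre-vaccination, so nothing in 11.8 is contradicted. Both points stand. A reader might infer that seroconversion is measured from the wrong baseline; the documents support only that the baseline is undefined and that the sole sample labelled for it is early.

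It can also be said that 49 to 52 days stacks every window at its limit, and that 16.1 expects a start-up lag of about one week for the two screening visits. The figure is indeed an upper bound. The one-week figure, however, is a recruitment planning assumption and does not limit the interval from Screening Visit 2 to Day 0.

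On infection, Exclusion 14 does apply at Day 0, its wording on the exempted visits can be read as allowing rescheduling, and adverse events are assessed at Screening Visit 2 and Day 0. Symptomatic illness is therefore partly captured; silent infection is not.

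Three further inferences are tempting and should be resisted:

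- That the whole primary outcome depends on this baseline. It does not; see Step 3.
- That the error would fall more on the metabolic syndrome group and hide a weaker response. The hypothesis in 11.3 concerns vaccine response and severity of infection, not how often infection occurs over a few weeks. The lay summary mentions susceptibility, but no document gives an infection rate by group.
- That each participant exposed in the gap shifts a group's seroconversion rate by 1/20 = 5 percentage points. That holds only if the classification actually changes, and only for the strain concerned. The documents give no exposure rate from which to count such cases.

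**Conclusion.** The point holds as a weakness of the sampling schedule and of the endpoint definition. As written, the only designated pre-vaccination antibody sample can precede vaccination by up to 49 to 52 days (42 to 45 if the one-week allowance is not added), and the visit supplying the baseline titer is not specified. The consequence is confined to seroconversion, by strain. The size and direction of any bias cannot be estimated from the documents, and no difference between cohorts is shown. The conclusion rests on the tube lists and windows in 11.7 being followed as written. If the laboratory already intends to use Day 0 serum, what remains is a missing definition, which the same edit supplies. It is a worthwhile, inexpensive improvement and does not put the study's design in doubt.

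**What to change.** In 11.8, define the baseline titer as the Day 0 value from blood drawn before the vaccine. In 11.7, under Study Visit 1, state that HI and neutralization will be run on an aliquot of the 10 ml serum already collected. Keep the Screening Visit 1 sample as back-up, to be used only when a Day 0 result is missing, and report how many participants rely on it and their gap in days.

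This takes the gap from baseline to vaccination to zero. Day 0 stays at 26.5 ml and the study total at 177.5 ml, with no added visit. The cost is slightly less Day 0 serum for cytokines; the documents do not give the volume each assay needs, so the laboratory should confirm that 10 ml is enough.

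If it is not, the antibody tube can be moved from Screening Visit 1 to Day 0. Day 0 becomes 36.5 ml, Screening 1 becomes 30.5 ml and the total remains 177.5 ml, but the back-up sample is lost. Adding a Day 0 tube while keeping the screening one would bring the total to 187.5 ml. The sample size of 20 per group is unaffected.

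One limit remains: a Day 0 baseline absorbs only a rise already present that day. It does not correct for infection whose antibody response appears later, or for exposure after vaccination.
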